## Data validation procedures

Data validation methods shall be appropriately applied as defined in the investigator's standard operating procedures (SOPs), which are part of an ISO 9001:2015-certified quality management system (QMS) operated and regularly updated by the investigator and audited by sponsors.

#### **Definitions of Study Variables**

| Event                                  | Study variable   | Operational definition   |
|--|------------------|--|
| Documentation
of medical
history | Age              | Age at index date  |
|  | Gender           | trivial  |
|  | Therapy          | Documentation of previous and current treatments and medications related to MS |
|  | Disease duration | Documentation of time since first MS diagnosis                                 |
| Assessment of                          | Relapse activity | Number of relapses within the last 12 months prior to enrollment               |

| inclusion and exclusion       | T2 lesion load                | Number of T2 lesions at time of assessment as defined by MRI   |
|-------------------------------|-------------------------------|--|
| parameters                    | New / enlarging T2
lesions | Number of new or one enlarging T2 lesions within the last 12 months prior to enrollment as defined by MRI  |
|                               | Gd-enhancing lesion           | Number of Gd-enhancing lesions within the last 12 months prior to enrollment as defined by MRI   |
| Assessment of clinical status | Therapy change                | Therapeutic regimen at the time of visit; therapy is subject to change   |
|                               | Relapse activity              | Number and time of relapses since last visit; assessment and documentation whether EDSS worsening is caused by relapses  |
|                               | Diagnosis                     | Documentation of current diagnosis   |
| Assessment of clinical scores | Disability                    | EDSS is used to quantify disability and disability progression over time in MS. Based on a neurological examination, 8 functional systems (visual, brain stem, pyramidal, cerebellar, sensory, bowel & bladder, cerebral, and other functions) are scored from 0 (no disability) to 5 or 6 (more severe disability). Ambulation is assessed based on the distance the patient is able to walk, whether assistance is required or restrictions are present. |
|                               | Disability progression        | Disability progression is defined as 1.0-point increase for patients with a baseline EDSS of 0 to 5.0, and 0.5 points for scores equal or higher than 5.5.   |
| Brain MRI
examination      | Thalamic volume               | CNN-based estimation of thalamic volume, adjustment for head size and age and normalization to a z score   |
|                               | Deep gray matter volume       | CNN-based estimation of deep gray matter volume, adjustment for head size and age and normalization to a z score   |
|                               | Whole brain volume            | CNN-based estimation of whole brain volume, adjustment for head size and age and normalization to a z score.   |
|                               | T2 lesion load                | CNN-based detection of T2 lesion with a minimum volume of 0.01 ml  |
|                               | New / enlarging T2 lesions    | CNN-based detection of new (minimum volume of 0.01 ml) and enlarging T2 lesions  |

## Outcomes/Endpoint Variables

Primary hypothesis and primary endpoint

The change of MS-related disability during a period of 24 months is inversely associated with the change of thalamus volume during the same period.

MS-related disability will be characterized by the Expanded Disability Status Scale (EDSS). The EDSS will be determined at inclusion (baseline), at 24 months after inclusion, and at additional visits at time intervals approx. every 6 months in between. The annual change of EDSS during the 24-month time period will be computed by linear regression of EDSS versus time including all visits. The change of thalamus volume will be determined in consecutive high-resolution T1w-MRI using a deep-learning based method developed and validated by JDX (Opfer et al. 2020). TVL will be calculated for each pair of two consecutive MRI scans using an advanced and validated method from Opfer et al (2020). The primary endpoint is the Pearson coefficient of the correlation between the annual change of EDSS and the annual change of the thalamus volume.

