## **Inclusion Criteria**

- MS, as diagnosed by the revised 2017 McDonald criteria
- Exhibiting a relapsing clinical course and history of brain MRI lesions consistent with MS
- Ages 18 to 55 years, inclusive
- Meet one of the following disease activity criteria
  - a. more than 10 T2 lesions at the time of the first visit OR
  - b. at least one documented relapse with the last 12 months prior to the first visit OR
  - c. documented evidence of at least 1 Gd-enhancing lesion on brain MRI within the last 12 months prior to the first visit OR
  - d. documented evidence of at least one new or one enlarging T2 lesion within the last 12 months prior to the first visit.

- Either receive or about to receive first-line oral immune therapies, such as teriflunomide, ozanimod, dimethylfumarate, ponesimod, and diroximethylfumarate.
- No intention to evaluate the patient to switch from first-line oral immune therapies to other therapy regimens.

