#### • Relapse activity assessment

A relapse is defined as the occurrence of new or worsening neurological symptoms attributable to MS and immediately preceded by a relatively stable or improving neurological state of at least 30 days. The new or worsening neurological symptoms must be accompanied by objective neurological worsening consistent with an increase of at least half a point on the EDSS, or 2 points on one of the appropriate FS scores, or 1 point on two or more of the appropriate FS scores. The change must be documented by the evaluator at either scheduled or unscheduled visits and must affect the FS scales that correspond to the

patient's symptoms (e.g., pyramidal, gait, cerebellar, brainstem, sensory, or visual). Symptoms must persist for > 24 hours and should not be attributable to confounding clinical factors (e.g. fever, infection, injury, adverse reactions to concomitant medications).

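### The EDSS slopes for the primary endpoint and S2 have no rule for scores taken during or soon after a relapse, so transient deficits count as disability change

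*Protocol*

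**What the plan says.** **Primary endpoint.** Section 3, Outcomes/Endpoint Variables, schedules the EDSS at baseline, at month 24 and "at additional visits at time intervals approx. every 6 months in between". The annual change "will be computed by linear regression of EDSS versus time including all visits". The Synopsis (Data Analyses), Statistical Analysis Methods and Missing data handling say the same. Then: "The primary endpoint is the Pearson coefficient of the correlation between the annual change of EDSS and the annual change of the thalamus volume".

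**Relapses.** Under Relapse activity assessment, a relapse needs objective worsening, for instance "consistent with an increase of at least half a point on the EDSS", and "The change must be documented by the evaluator at either scheduled or unscheduled visits". One route to entry (Inclusion Criteria) is "at least one documented relapse with the last 12 months prior to the first visit"; no relapse-free interval before the baseline EDSS is required. Definitions of Study Variables has sites record the number and timing of relapses, with "assessment and documentation whether EDSS worsening is caused by relapses". No endpoint or analysis in the protocol uses that record, and relapse during follow-up is not listed under Other Co-variates/Control Variables.

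**Progression.** "Disability progression is defined as 1.0-point increase for patients with a baseline EDSS of 0 to 5.0", and 0.5 points from 5.5 upward, with no confirmation step. S1 has two definitions. Secondary hypotheses and secondary endpoints dichotomizes the annual EDSS change; Statistical Analysis Methods uses the individual increase at month 24, with the word confirmed only in brackets. S2 fits a slope to months 24, 30 and 36 and applies the S1 cut-off.

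**Imaging side.** Bias/confounding and effect modification excludes MRI data acquired less than 6 months after a therapy switch, because of pseudo-atrophy. The EDSS has no comparable rule.

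**The concern.** The research question is whether thalamic loss drives disability progression. A relapse deficit that later resolves is not progression, yet as written its score enters the slope with full weight. Late in follow-up it looks like worsening. At baseline or month 6 it looks like improvement. In the three-visit S2 slope it can decide the outcome by itself.

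The protocol already separates relapse-related worsening at data capture and removes a comparable transient artefact on the MRI side of the same correlation. The gap is therefore in the analysis, not in the data collected. At stake are the meaning of the primary outcome variable, some precision in a correlation expected to be only 0.15, and the S1 and S2 classifications.

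**Working it through.** **1. The plan's own figures (Power/Sample Size).** Expected r = 0.15, two-sided type I error 0.05, power 0.80:

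n = ((1.960 + 0.842) / atanh(0.15))² + 3 = (2.802 / 0.1511)² + 3, which rounds up to 347. This agrees with the protocol. S2 (about 0% versus 5%) also reproduces, at 152 per group. S1 gives 197 for the larger group against 196 stated, with 79.9% power at 196/98. The sample sizes are not in dispute.

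**2. Weight of one visit in the primary slope.** A score at time t contributes (t - mean t)/Sxx per point. For 0, 0.5, 1, 1.5 and 2 years, the mean is 1 and Sxx = 1 + 0.25 + 0 + 0.25 + 1 = 2.5.

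| Month | 0 | 6 | 12 | 18 | 24 |
|---|---|---|---|---|---|
| Slope shift per 1.0 point (per year) | -0.4 | -0.2 | 0 | +0.2 | +0.4 |

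A steady 1.0-point worsening over 2 years is 1.0/2 = 0.5/year. One fully reversible 1.0-point rise at month 24 adds 0.4/year; at baseline it subtracts 0.4/year; at month 12 it has no effect.

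**3. S2 slope.** For 2, 2.5 and 3 years, Sxx = 0.25 + 0 + 0.25 = 0.5, so the weights are -1.0, 0 and +1.0 per year.
- A transient 1.0 point at month 36 alone gives 1.0/year, which meets the 1.0 cut-off applied to the annual slope.
- The same rise at month 24 gives -1.0/year and can hide real progression.

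**4. S1 under its two definitions.**
- Increase from baseline at month 24, unconfirmed: a transient 1.0 point (0.5 from baseline 5.5 upward) is enough.
- Annual slope with five visits: a single raised month-24 score needs 1.0/0.4 = 2.5 points for the 1.0 cut-off.

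**5. Effect on the primary correlation (illustrative).** Let f be the share of slope variance that is relapse noise unrelated to thalamic loss. The document does not give f. Then r = 0.15 × √(1 - f), and power = Φ(atanh(r) × √(n - 3) - 1.96).

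| f (assumed) | r | Power, n = 347 | Power, n = 433 |
|---|---|---|---|
| 0 | 0.150 | 80% | – |
| 10% | 0.142 | 76% | 84% |
| 20% | 0.134 | 71% | 80% |
| 30% | 0.125 | 65% | 74% |

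The 433 is the number that Overview patient attrition projects for month 24.

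**6. Effect on S2 (illustrative).** Suppose 2% of non-progressors in each group were classed as progressors through a relapse score alone. The rates become 2% and 0.05 + 0.95 × 0.02 = 6.9%. At 152 per group the standard errors are 0.02365 (pooled) and 0.02349 (unpooled), so power = Φ((0.049 - 1.96 × 0.02365)/0.02349) = Φ(0.112), about 54%. The 2% is an assumption.

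**The case against.** Several objections carry weight.

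- **S1.** A reader might infer that one relapse score settles S1. That holds only under the increase-from-baseline wording without confirmation. Under the annual-slope wording about 2.5 points are needed, and confirmation, once defined, could remove transient rises.
- **Extra visits.** A reader might infer that relapsing patients add further high scores from unscheduled visits. The mention of such visits concerns documenting a relapse; the time and events schedule has no unscheduled EDSS column. The point stands on scheduled visits alone.
- **Power.** A reader might infer a definite power shortfall. Relapse rate, size and duration of the rise, and slope variance are not in the document. The 0.15 is taken by order of magnitude from a published brain-volume correlation; if that figure already contained relapse scores, the loss would be counted twice. If relapses and thalamic loss share inflammatory activity, r could be inflated instead.
- **S1 false-positive rate.** With an assumed 0.2 relapses/year, about 0.2 × 0.25 = 5% of patients would be within 3 months of a relapse at month 24. It is tempting to set this against the 5% progression assumed for group 1. But a relapse may involve only half a point or functional-system changes, so being near a relapse is not the same as being 1.0 above baseline.
- **Estimand.** The primary objective is change in MS-related disability, not relapse-independent progression, and incomplete recovery is genuine change. This is fair, and is the reason to keep the all-visits analysis alongside.
- **SAP.** An unseen SAP could use the relapse record, but to exclude scores it would have to depart from the all-visits rule that the protocol fixes.

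**Conclusion.** The point holds for the primary slope and S2: following the protocol as written counts transient relapse deficits as disability change. The shifts of ±0.4/year at the ends of the 24-month slope and ±1.0/year in S2, per 1.0 point, follow from the nominal visit schedules alone. The error runs in both directions.

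For S1 the point is conditional. The document holds two definitions that must be reconciled, and an undefined confirmation.

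The loss of power is not established. The 76-65% at n = 347 rests on an assumed f of 10-30% and on relapse noise being independent of thalamic loss; at 433 the same assumption gives 84-74%. Neither the size nor the direction of the net effect on r can be settled from the protocol. It therefore does not follow that the sample size is wrong or that the study will miss its primary endpoint.

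**What to change.** Analysis wording only:

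1. **Primary slope.** In the Synopsis (Data Analyses), Outcomes/Endpoint Variables, Statistical Analysis Methods and Missing data handling, fit the slope to all EDSS assessments except those within a prespecified window after onset of a documented relapse. A window of 90 days is an example, not a figure from the document. Report the all-visits slope and other window lengths as sensitivity analyses.
2. **S2.** Add the same exclusion to the regression sentence in both places where S2 is described. Do not annualise a slope from two visits 6 months apart: there Sxx = 0.125, the weight is 0.25/0.125 = 2.0 per year, and a half-point step alone gives 1.0/year. Use the first EDSS after the window where one exists; otherwise treat the S2 outcome as missing.
3. **S1.** Reconcile the annual-slope and increase-from-baseline definitions, define confirmed, and apply the same exclusion to the classification.

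Relapse timing is already collected, so no new data are needed. The cost is a few EDSS points and occasionally a patient. Some lasting relapse-related worsening near month 24 may also be left out, which the all-visits sensitivity analysis would show.

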#### Other Co-variates/Control Variables

| Total intracranial volume (TIV) | most regions-of-interest (such as the thalamus) in the brain, MRI-based     |
|---------------------------------|---|
|                                 | volume estimates are associated with TIV. Careful adjustment for TIV is     |
|                                 | required to improve the statistical power and to avoid spurious effects and |
|                                 | misinterpretation of actual effects.  |
|                                 | -   |

| Age and sex   | Regional brain volumes are strongly correlated with age and sex.   |
|---|--|
| Disease duration  | EDSS and MRI-based volume estimates are associated with disease duration (time since diagnosis). Treatment may affect TVL, new lesions, and disability worsening. Mitigation may be to use treatment as a covariate in statistical analysis.   |
| Baseline parameters used to
define inclusion, such as T2
lesion load, Gd-enhancing
lesions, new/enlarging T2 lesions | All these parameters could have a confounding effect and are thus to be controlled.  |
| EDSS at baseline  | EDSS at baseline is also a predictor for disability progression and should be controlled.  |
| Treatment regimen   | EDSS and MRI-based volume estimates are associated with disease duration.  Treatment may affect TVL, new lesions, and disability worsening.  Mitigation may be to use treatment as a covariate in statistical analysis.  Treatments are first-line oral immune therapies such as teriflunomide, ozanimod, dimethylfumarate, ponesimod, and diroximethylfumarate. |

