# Primary objective: To demonstrate that the change of MS-related disability during a period of 24 months is inversely associated with change of thalamus volume during the same period.

In a previous project sponsored by Celgene, the investigators in this study developed and validated a technique that allows reliable and robust calculation of change in regional volumes based on a longitudinal approach in high-resolution T1w MRIs (Opfer et al. 2020). Such an approach allows percentage estimation of volume change of corresponding regions in successive high-resolution T1w MRIs and is much less susceptible to noise than conventional methods based on calculation of absolute volumes at different time points and a regression model to estimate volume change. It has the potential to overcome the technological limitations that hindered the work of Eshaghi et al. (2018).

[figure not shown]

Figure 3. Linear regression of all EDSS measurements

With this approach, it is methodologically feasible to assess TVL and deep GMVL for individual MS patients.

MS-related disability will be characterized by the Expanded Disability Status Scale (EDSS). The EDSS will be determined at inclusion (baseline), at 24 months after inclusion, and at additional visits at time intervals approx. every 6 months in between. The annual change of EDSS during the 24 months' period will be computed by linear regression of EDSS versus time including all visits (Fig. 3). The slope of the regression line will be the annual change of EDSS.

[figure not shown]
For the correlation analysis annual change of EDSS and annualized TVL will be considered as continuous variables. For all study subjects three high-resolution T1w-MRI scans will available. TVL will be calculated for each pair of two consecutive MRI scans. Annualized TVL between the baseline (BL) and last follow-up (FU) scan will be calculated by multiplying the TVL between the two consecutive scans and dividing the resulting TVL with the time interval between BL and FU scan.

A Pearson correlation analysis will be used to test for with a significance level of p = 0.05. Outcomes can be modelled both as dichotomous (CDP – yes, no) and continuous (raw EDSS score) variables. In case of dichotomous variables, a logistic regression will be used.

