#### **Power/Sample Size**

#### Primary objective

We want to show whether the correlation between the change in MS-related disability and the change in thalamic volume is different from zero. Both the change in MS-related disability and the change in thalamic volume are continuous variables. We will use Pearson's correlation analysis. The expected correlation coefficient is 0.15, which seems to be a reasonable assumption at this point because the correlation coefficient between change in MS-related disability and change in total brain volume published recently by Uher et al. (2021) is of the same order of magnitude.

Assuming a type I error of 0.05 and a type II error of 0.20, we estimate the required sample size to be 347 (24 months after baseline EDSS measurement). Considering an annual dropout rate of 15% the total required sample size is approximately 600 study participants.

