#### 5. STUDY LIMITATIONS/STRENGTHS

#### Generalizability of study results

The PENTAGON study if pursued over the full length is able to link results of the phase III clinical trials (RADIANCE and SUNBEAM) regarding the effect of ozanimod on brain volume, and in particular TVL to disability progression in a real world setting. Once confirmed pathological TVL could be considered an independent risk factor for disability worsening. This would then justify inclusion of TVL into the spectrum of treatment targets in MS.

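### The primary test is fixed as an unadjusted Pearson correlation, although the protocol names covariates to be controlled; it can show crude association but not an independent role for thalamic volume loss

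*Protocol*

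**What the plan says.** In Outcomes/Endpoint Variables, "The primary endpoint is the Pearson coefficient of the correlation between the annual change of EDSS and the annual change of the thalamus volume". The primary-objective part of Statistical Analysis Methods repeats this as the test: "A Pearson correlation analysis will be used to test for with a significance level of p = 0.05". No covariate appears in either place, nor in the Synopsis. A logistic regression is mentioned there for a dichotomised outcome, also without covariates.

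Power/Sample Size uses the same quantity. The hypothesis is "We want to show whether the correlation between the change in MS-related disability and the change in thalamic volume is different from zero". The input is "The expected correlation coefficient is 0.15, which seems to be a reasonable assumption at this point", and the result is "Assuming a type I error of 0.05 and a type II error of 0.20, we estimate the required sample size to be 347".

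Other Co-variates/Control Variables differs in strength from row to row:

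- Baseline inclusion parameters (T2 load, Gd-enhancing lesions, new or enlarging T2 lesions): "All these parameters could have a confounding effect and are thus to be controlled".
- Baseline EDSS: "EDSS at baseline is also a predictor for disability progression and should be controlled".
- Intracranial volume: careful adjustment is described as required.
- Age, sex and disease duration: listed with a remark on their association with volumes (and, for disease duration, EDSS), but with no explicit instruction to control.
- Treatment: a covariate that may be used. The section on bias and confounding says the same and adds that treatment imbalance between the volume-loss groups can bias results.

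On interpretation, Study Rationale asks how far TVL is an independent driver of progression. Research Question speaks of a driver and a treatment target. Generalizability of study results says "Once confirmed pathological TVL could be considered an independent risk factor for disability worsening".

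**The concern.** This is a non-randomised cohort of patients aged 18 to 55, on several oral therapies and selected partly on lesion activity. Age, disease duration, lesion burden and therapy can plausibly act on both EDSS slope and TVL, and the protocol itself treats several of them as confounders. Yet the analysis that carries the primary conclusion uses none of them.

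The only covariate list attached to a named analysis belongs to the S2 prediction model, which concerns months 24 to 36. The residual method for age and intracranial volume is described for volumes at one time point, not for the longitudinal TVL in the primary endpoint.

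The assumed correlation is small, so a modest shared cause is of the same order as the effect sought. If it acts in the same direction on both changes it can produce a significant crude r; if in opposite directions it can mask a real link. What is at stake is what a significant result may be said to mean.

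**Working it through.** **1. The plan's own figure.** Inputs from Power/Sample Size: r = 0.15, type I error 0.05, type II error 0.20. With Fisher's z:

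n = ((1.960 + 0.842) / atanh(0.15))² + 3 = (2.802 / 0.1511)² + 3 = 346.6, so 347.

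The stated 347 reproduces exactly as a two-sided test with no covariates (one-sided gives 274). The sample size therefore confirms that the primary test is the crude one.

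**2. Smallest significant correlation.** tanh(1.960/√(n − 3)) is 0.105 at n = 347. At n = 433, the month-24 number in the attrition table (600 × 0.85²), it is 0.094.

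**3. Effect of one omitted factor (illustration).** Assume a factor correlated q with both EDSS slope and TVL, and no direct link between the two. The documents give no value for q. The crude correlation is then q². With m = atanh(q²)·√(n − 3), the test rejects with probability Φ(m − 1.96) + Φ(−m − 1.96).

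| q with both | crude r | n = 347 | n = 433 |
|---|---|---|---|
| 0.10 | 0.010 | 5.4% | 5.5% |
| 0.15 | 0.0225 | 7.0% | 7.5% |
| 0.20 | 0.040 | 11.5% | 13.2% |
| 0.30 | 0.090 | 38.8% | 46.5% |

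Simulation with 4,000 runs per setting gave 12.3% and 13.4% at q = 0.2, and 38.5% and 46.4% at q = 0.3. The partial correlation given the factor rejected in 4.4% to 5.5% of runs across the settings simulated.

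**4. Price of adjustment if the adjusted r is still 0.15.** Take k = 12 covariate degrees of freedom: age, sex, intracranial volume, disease duration, baseline EDSS, three lesion parameters, and four for the five named drugs.

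- Required n = 346.6 + 12 = 358.6, so 359. For k from 5 to 15 it is 352 to 362.
- Enrolment: 359/0.85² = 497 at 15% annual dropout and 359/0.80² = 561 at 20%, both within 600.
- Power at n = 433: 0.1511 × √418 − 1.96 = 1.13, giving 87.1%, against 88.0% unadjusted. At n = 347 it is 78.6% against 80.0%.

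**5. Price if part of the 0.15 is confounding.** With the same single factor, the partial correlation is (0.15 − q²)/(1 − q²).

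- q = 0.2: 0.11/0.96 = 0.115. Power with k = 12 is about 65% at n = 433 and 55% at n = 347.
- q = 0.3: 0.06/0.91 = 0.066. Power is about 27% and 23%.

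The confounding that makes the crude test misleading therefore also makes the adjusted test costly.

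**The case against.** **The test matches its hypothesis.** The primary objective claims association and the null is zero correlation. If a shared cause makes the true crude correlation 0.04 or 0.09, rejecting that null is correct. A reader might infer from the table that the planned test has an inflated type I error; it does not. Those percentages are error rates only for a claim of a direct or independent effect. This part of the objection stands.

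**The covariate section names no analysis, and detail of this kind commonly goes into the SAP.** This stands in part. The section is explicit only for the inclusion parameters, baseline EDSS and intracranial volume; reading it as an order to control every listed factor goes too far, above all for treatment. But the protocol fixes the endpoint itself as the crude coefficient and sizes it so. An SAP could add an adjusted analysis, but could not make it primary without departing from that definition.

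**Independence is addressed elsewhere.** S1 restricts to patients with normal whole-brain loss, the S2 model includes clinical covariates, and the independent-risk-factor sentence is conditional and concerns pathological TVL. All true. But S1 is an unadjusted chi-square test that deals only with whole-brain loss, and S2 covers a later period that is reached only if the study is extended.

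**The upper illustrations are strong.** At 0.2 or 0.3 the factor would correlate more closely with EDSS slope than TVL is assumed to. That is fair, and it is why 0.10 and 0.15, where little happens, are shown as well.

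**Adjusting for baseline EDSS is contestable.** It is one of the points used to fit the slope, so its measurement error is tied to the outcome. This stands and is met in the fix by a sensitivity analysis.

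**Conclusion.** The point holds as a mismatch between the primary analysis and both the protocol's own statements on control and its intended interpretation. The crude Pearson test is valid for unadjusted association; it cannot show that TVL is an independent driver or risk factor.

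A reader might go further and infer that a significant result would be confounding alone. The documents do not support that, because they give no confounder strengths: the rate of rejection without a direct link runs from about 5% to 39% at n = 347 as the assumed correlation with both changes goes from 0.10 to 0.30. A reader might equally infer that adjustment is almost free. That is so only if the adjusted correlation is still 0.15.

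The figures rest on a single confounder correlated equally with both changes, the Fisher approximation, and about 12 covariate degrees of freedom.

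**What to change.** Prespecify a linear regression of annual EDSS change on annualised TVL (equivalently a partial correlation), adjusted for age, sex, disease duration, baseline lesion parameters, baseline treatment and baseline EDSS. Add a sensitivity analysis without baseline EDSS. State whether intracranial volume enters. Make this analysis the basis of any independence claim and report the crude Pearson r beside it. If the crude Pearson stays primary, limit its conclusion to unadjusted association and reword the limitations section accordingly. In either case, say which analyses the listed control variables apply to.

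The cost is protocol as well as SAP wording, because the protocol defines the endpoint. The covariates are already among the study variables. Gadolinium is given at the physician's or radiologist's discretion, however, so the Gd-lesion covariate will need a rule for patients scanned without it. Baseline treatment as a covariate does not deal with switches during follow-up.

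Statistically the price is about 12 degrees of freedom (n = 359 instead of 347; power 87% instead of 88% at 433) if the adjusted r is 0.15, and a real loss if it is smaller (about 65% at 433 for 0.115). The value 0.15 should therefore be restated and justified as an adjusted correlation.
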